#### *Secondary outcomes*

Outcomes related to gluten exposure will be considered as continuous variables and also converted to categorical variables. The per individual change in frequency of gluten exposure will be determined by calculating the difference in the proportion of GIP positive urine samples in the pre-randomization (weeks 1, 2, and 4) and post-randomization (weeks 8 through 30) samples. The same visits will be used to calculate the per individual change in mean quantity of gluten exposure pre- and post-randomization. Results will be categorized as decreased, no change or increased frequency/mean concentration of gluten exposure.

Symptom and quality of life scores are also continuous variables and group comparisons will be assessed using a paired t-test. The PedsQL 4.0 Generic Subscales has 23 items across four subscores (physical, emotional, social and school functioning) and scores are scaled to range from 1 to 100. The scale has been validated for children aged 5 to 18 and the minimally clinically important difference (MCID) is 4.4 for child report and 4.5 for parent report. The CDDUX has 12 items and three subscores related to diet, communication and having celiac disease. It is also scaled from 1 to 100 and has been shown to correlate with perceptions of disease severity.

Agreement between results of patient/parent performed qualitative testing and quantitative testing performed by research team will be assessed using McNemer's test (qualitative testing) or intraclass correlation (quantitative testing).

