The next phase of the study will occur primarily at home. During the 7 week run-in phase, participants will collect urine specimens and complete symptom questionnaires at 2 random intervals when prompted by the study co-ordinator. During week 8, there will be a study visit with the research staff. Participants will return samples collected at home along with an additional stool sample collected at week 8 which will be used for randomization to either continued double-blinding to biomarker detection or an open results arm. All participants will have a diet assessment in conjunction with the week 8 study visit. This will occur either in person or remotely by telephone or video link. During the last phase of the study (weeks 8-30), participants will be prompted to collect additional urine specimens and complete questionnaires at random intervals (~q 4 weeks). Participants in the open arm may also collect up to 4 additional stool samples during this time as well.

Participants in the open results arm will also be provided with home testing kits so that they may receive immediate qualitative (yes/no) feedback regarding the presence of biomarkers of gluten exposure in their stool and/or urine. Collection of urine samples will be initiated by the investigators. Collection and testing of stool samples will occur at times of the participants choosing. Participants may opt to test up to 4 stool samples, and will report test use date, results of the test, and reasons for use to the research team after each use. At the end of the 30 week study period, all participants will have a final study visit and an additional diet assessment by a Registered Dietitian. All participants will be unblinded to the results of biomarker testing after their samples have been processed. Blood will be collected and stored for testing of biomarkers of gluten-free diet adherence at the first study visit. If a participant agrees to blood sample collection at their third study visit, blood will also be collected at that time (weeks 0, and 30).

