##### Secondary outcomes:

- Difference in mean gluten exposure following randomization in blinded vs. open results groups. Mean gluten exposure is defined as the average per individual subject post-randomization concentration of gluten immunogenic peptides detected using the quantitative assay.
- Per individual change in frequency and quantity of gluten exposure pre- and post-randomization in blinded and open results groups.
- Symptom score (average for weeks 8 through 30 and at week 30) with blinded vs. open results of biomarker detection.

- Symptom score (average during run-in compared to week 30) with blinded vs. open results of biomarker detection.
- Change in celiac disease specific quality of life as measured by CDDUX between weeks 1 and 30 in blinded vs. open results groups.
- Change in health related quality of life between weeks 8 and 30 as measured by PedsQL core 4.0^37 in blinded vs. open results groups.
- Growth trajectory (weight, height and BMI) between weeks 8 and 30.
- Agreement between results of patient/parent performed qualitative testing and quantitative testing performed by research team
- Rate of school absences and missed extracurricular activities in blinded vs. open results group.

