**(5) Data Collection Methods, Assessments, Interventions and Schedule (what assessments performed, how often)**

This randomized, partially double-blinded study will involve three study visits as well as home questionnaires, urine and stool collection, and diet assessment by a Registered Dietitian. The first study visit is in conjunction with a scheduled outpatient clinic appointment for follow-up of celiac disease. There will be additional visits with the study coordinator at randomization (week 8) and study completion (week 30). The interval between the first and second study visits is a run-in period to allow for behavior modification in response to the clinician assessment and/or participation in a study where adherence will be monitored. A dietitian assessment will be conducted by a Registered Dietitian at randomization (week 8) and at the end of the study (week 30). At each study visit, participants/caregivers will be asked to complete symptom and quality of life questionnaires. Blood may be collected and stored for testing for biomarkers of gluten-free diet adherence, celiac disease activity and nutrition at the initial and final study visits. Throughout the study period, participants will maintain a diary of suspected and probable gluten exposures.

During weeks 2 through 7 (between the first and second study visits), when prompted by the study coordinator, participants will collect their next urine at home and to complete the symptom questionnaire. Participants will be blinded to the exact timing of sample collection. This method will be employed throughout the study period to ensure that sample collection reflects usual behavior and to reduce the Hawthorne Effect due to participants adjusting their eating behaviors in anticipation of observations being collected.

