#### **(6) Study Timeline (as applicable)**

- Eligibility Screening
  - Participants who are eligible for this study will be identified when they are scheduled for an outpatient clinical appointment for follow-up of celiac disease
  - Potential participants will be contacted and informed of the study. If they express that they may be interested in participating, they will be asked to provide verbal consent to receive sample collection materials and a copy of the consent form.
  - urine sample (from a first morning void if possible) will be collected. Optional stool sample collected.
- Recruitment Visit (week 1) in conjunction with a scheduled outpatient clinic appointment for follow-up of celiac disease
  - written informed consent
  - provide stool and urine samples (may be collected prior to visit)
  - patient/parent self-report questionnaire
  - height and weight
  - blood draw: TTG, DGP, CBC, stored samples for makers of gluten-free diet adherence, celiac disease activity and nutrition.
  - Participant receives a parking voucher
- At home (weeks 1 through 7)
  - collect additional urine samples and complete questionnaire when contacted by study coordinator at random intervals (x2)
  - keep a diary of suspected/probable gluten exposures.
  - collect an additional stool sample during week 8 (to be used at week 8 study visit for randomization)
- Study Visit 2: (week 8)
  - Return samples and questionnaires completed at home when prompted.
  - Bring additional stool sample collected during week 8 (for randomization)
  - Randomization to blinded or open test results.
  - patient/parent self-report questionnaires
  - height and weight
  - Participant receives parking voucher and \$30 ClinCard as a token of appreciation
  - Diet assessment, either in person or remotely by telephone or video link
- At home (weeks 8 through 30)
  - collect additional urine samples and complete questionnaire when contacted by study coordinator at random intervals (x6, approximately every four weeks)
  - keep a diary of suspected/probable gluten exposures
  - Use of stool kits at participants discretion (x0-4)

- Final study visit (week 30)
  - Return samples and questionnaires completed at home.
  - Complete quality of life and symptom questionnaires.
  - Diet assessment, either in person or remotely by telephone or video link.
  - Height and weight

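### The baseline for change in GIP is fixed to urine from weeks 1, 2 and 4, but run-in urine is collected at two random times, so the rule as written drops valid pre-randomisation samples

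*Protocol*

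**What the plan says.** Protocol section H (Data Analysis Plan, Secondary outcomes) defines the change in frequency of gluten exposure as the difference between "the proportion of GIP positive urine samples in the pre-randomization (weeks 1, 2, and 4) and post-randomization (weeks 8 through 30) samples". It then adds: "The same visits will be used to calculate the per individual change in mean quantity of gluten exposure pre- and post-randomization". Each child is to be classed as decreased, unchanged or increased.

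The collection schedule is set in three other places:

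- Section D(3), on the run-in: "participants will collect urine specimens and complete symptom questionnaires at 2 random intervals when prompted by the study co-ordinator".
- Section D(5) gives the window: "During weeks 2 through 7 (between the first and second study visits), when prompted by the study coordinator". It adds that participants are not told the timing in advance, so that samples reflect usual behaviour.
- Section D(6) heads the same home phase as weeks 1 to 7, again with two prompts at random intervals.

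The only other planned urine before randomisation is the enrolment sample, preferably a first-morning void. It may be collected before the visit or, for families not reached beforehand, at home afterwards.

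On a related baseline, section D(4) measures change in CDDUX "between weeks 1 and 30 in blinded vs. open results groups", but PedsQL change and growth from week 8 to week 30. Section D(5) has quality of life questionnaires completed at every study visit.

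**The concern.** The analysis rule names time points that the schedule does not generate. There is no visit or fixed collection in week 2 or week 4, although section H speaks of visits. An analyst who follows section H must discard prompted samples from weeks 3, 5, 6 and 7. One who follows the evident intent must depart from the written rule. Unless the text is reconciled, the baseline could be chosen after the data are seen.

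A child with neither prompted sample in the named weeks is left with the enrolment sample alone. That baseline can only be 0% or 100%. A child at 0% cannot then be classed as decreased, nor a child at 100% as increased, so the three-way classification is partly determined by which single sample survived.

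**Working it through.** The plan gives no figure on this point to reproduce. The check sets the sections against each other and then sizes the loss under stated assumptions.

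1. **Planned baseline samples.** One enrolment urine plus two prompted urines makes three (sections D(3), D(5), D(6)). Section H also lists three weeks, but the schedule fixes only the first of them.

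2. **Prompts in two different weeks, evenly drawn from weeks 2 to 7 (assumed).** There are C(6,2) = 15 pairs.
   - Both in weeks 2 and 4: 1/15 = 6.7%.
   - Exactly one in week 2 or 4: 2 × 4 / 15 = 8/15 = 53.3%.
   - Neither: C(4,2)/15 = 6/15 = 40%.
   - Expected prompted samples kept: 2 × 2/6 = 0.67 of 2. With the enrolment sample, 1.67 of 3, or 56%.

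3. **Other assumptions.**
   - Independent prompts over weeks 2 to 7, same week allowed: neither falls in week 2 or 4 in (4/6)² = 44.4%; both do in (2/6)² = 11.1%. The mean is again 0.67 of 2.
   - Different weeks over weeks 1 to 7, C(7,2) = 21 pairs, counting weeks 2 and 4 only: both 1/21 = 4.8%, neither 10/21 = 47.6%, mean 2 × 2/7 = 0.57 of 2.
   - The same, but also counting a prompt that falls in week 1: both 3/21 = 14.3%, neither 6/21 = 28.6%, mean 2 × 3/7 = 0.86 of 2.

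   Across these cases, 1.57 to 1.86 of the 3 planned samples are usable.

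4. **Effect on a child's baseline.** The within-person standard error of a proportion from k samples is √[p(1 − p)(1 − ICC)/k]. With p = 0.5 and ICC = 0.6, both borrowed from the protocol's power section, the numerator is 0.25 × 0.4 = 0.10. This gives 0.316 for one sample, 0.224 for two and 0.183 for three.

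5. **CDDUX interval.** With equal variances at each visit, a change score has variance 2σ²(1 − r). The ratio of a week 1 to 30 change to a week 8 to 30 change is (1 − r₁)/(1 − r₈), where r₁ and r₈ are the correlations of week 1 and week 8 with week 30. The protocol gives neither. Assumed pairs (r₁, r₈): 0.6 and 0.6 give 1.0; 0.4 and 0.5 give 1.2; 0.5 and 0.6 give 1.25; 0.5 and 0.7 give 1.67.

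**The case against.** The strongest reply is that the three weeks in section H are an outdated label for the three planned urines, and that the operative word is pre-randomisation. On that reading nothing is lost. This may well be the intent, and it is why the repair is small. It does not rescue the text, which lists specific weeks and reuses them for mean quantity. If coordinators in fact prompt in weeks 2 and 4, no sample is lost, but then the random timing in section D is what is misdescribed. Either way the sections must be reconciled. Leaving detail to a statistical analysis plan is no answer either, because the protocol has already stated a rule.

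A reader might go further and infer that the enrolment urine should be removed because it precedes the run-in, whose purpose is stated: "The interval between the first and second study visits is a run-in period to allow for behavior modification in response to the clinician assessment". The documents do not support that as the main analysis. The prompted samples also fall within the run-in, so removing the enrolment sample would not remove the run-in effect. It would raise the within-person standard error from 0.183 to 0.224, about 22%, for every child with complete data. The difference in void type and timing is real but common to both arms, and a sensitivity analysis is enough for it.

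A reader might also infer that the symptom average for weeks 8 to 30 contains a baseline score, or that the week-8 questionnaires follow disclosure of the allocation. Neither is established. The power section uses weeks 8 through 30 as its label for the post-randomisation phase, and the visit list in section D(6) need not be chronological.

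**Conclusion.** The point holds as a contradiction within the protocol: the baseline weeks in section H do not match the run-in collection described in sections D(3), D(5) and D(6). It affects two secondary outcomes, change in GIP frequency and change in mean quantity. Under even prompting over weeks 2 to 7, 40% of children keep no prompted sample in the baseline and 6.7% keep both. These percentages rest on an assumed prompting pattern; the contradiction does not.

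It would be too strong to say that most baseline data are lost. That is true of the prompted samples (0.67 of 2 kept), but with the enrolment sample a little over half remain (1.67 of 3). Nor is the comparison between arms biased: which samples count is settled before randomisation and in the same way for both groups. The primary outcome and the sample size rest on post-randomisation urine and are untouched.

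The week-1 start for CDDUX is a valid pre-randomisation choice, not an error. Starting at week 8 would match PedsQL and growth and keep shared run-in change out of the score. The gain in precision ranges from none (ratio 1.0) to appreciable (1.67), depending on correlations that the protocol does not give.

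**What to change.** In section H, replace the listed baseline weeks with: *all urine samples collected before randomisation (the enrolment sample and the two prompted run-in samples, whatever the week)*. State that the same set is used for change in mean quantity, and refer to samples rather than visits. Align the run-in window between section D(5) (weeks 2 to 7) and section D(6) (weeks 1 to 7).

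Add a sensitivity analysis in which the baseline uses only the prompted run-in samples, to address the enrolment sample's void type and timing.

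Optional and minor: in section D(4), measure CDDUX change from week 8 to week 30, as for PedsQL.

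The cost is a few words in sections H and D. No visit, sample, sample size or primary analysis changes. The sensitivity analysis has a noisier baseline, with two samples per child instead of three.

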### **I. Statistical Power and Sample Considerations**

The primary outcome is the difference in rate of gluten detection in the six urine samples provided after randomization (weeks 8 through 30) between the blinded and unblinded groups. A total sample of 102 (n=51 in each group) provides 90% power to detect a difference of 50% gluten detection in the blinded group versus 25% gluten detection in the open results group, given six outcomes per participant with an intraclass correlation of 0.6 and alpha set at 0.05. Given a more conservative intraclass correlation of 0.8, we will still have 82% power to detect the predicted effect size. If participants are more highly adherent, then this sample size should also be sufficient as fewer participants will be required. For example, using the same assumptions for intraclass correlation, with 43 subjects in each group there is 90% power to detect a difference of 40% gluten detection in the blinded versus 25% gluten detection in the open results group (alpha = 0.05).

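### Labelling each child's exposure as decreased, unchanged or increased from 3 run-in and 6 later urines, with no margin given for no change, would let sampling noise read as change

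*Protocol*

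**What the plan says.** Section D(4) of the Protocol lists as a secondary outcome: "Per individual change in frequency and quantity of gluten exposure pre- and post-randomization in blinded and open results groups". Section H (Secondary outcomes) defines the change in frequency by "calculating the difference in the proportion of GIP positive urine samples" between "pre-randomization (weeks 1, 2, and 4) and post-randomization (weeks 8 through 30) samples". The same visits serve for the change in mean concentration. The section then adds: "Results will be categorized as decreased, no change or increased frequency/mean concentration of gluten exposure". No cut-off separates no change from the other two labels.

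The same paragraph opens with "Outcomes related to gluten exposure will be considered as continuous variables and also converted to categorical variables", so the numerical change is kept beside the labels. Section I and the study timeline in section D(6) both plan six post-randomization urines. The comparison is therefore of a proportion out of 3 with a proportion out of 6.

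**The concern.** With k positives of 3 before randomization and j of 6 after, the two proportions are equal only when j = 2k. Few outcomes meet that condition, so a child whose underlying exposure rate never moves can easily be labelled changed. On mean concentration, two averages of a continuous assay will in practice tie only when all nine samples are non-detects. The unequal counts also raise the question of whether the label leans in one direction.

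The outcome is worded per individual and reported in each group. A table of labels by arm invites statements such as the share of children who improved with open results, and much of that share could be chance. A comparison of arms that used the labels would also give up information that the numerical change retains.

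**Working it through.** **Inputs.** There are 3 pre-randomization urines (section H) and 6 post-randomization urines (section I). Detection is 50% in the blinded arm and 25% in the open arm, the intraclass correlation (ICC, ρ) is 0.6 with 0.8 as the alternative, and there are 51 children per arm (all section I). Three inputs are assumptions: any non-zero difference counts as change, all nine samples are present, and each child keeps one true rate throughout.

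**1. The plan's own figure.** The effective number of samples per arm is 51 × 6 / (1 + 5ρ).
- ρ = 0.6: 306 / 4 = 76.5. Two-sided 5% power for 50% v 25% is 0.899, against the stated 90%.
- ρ = 0.8: 306 / 5 = 61.2. Power is 0.823, against the stated 82%.

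Both reproduce, so these rates and correlations are a fair basis for the check.

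**2. Frequency label with no true change.** Let each child's rate follow a beta distribution with α = p(1−ρ)/ρ and β = (1−p)(1−ρ)/ρ. Then

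P(a of 3, b of 6) = C(3,a) · C(6,b) · B(α+a+b, β+9−a−b) / B(α,β),

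and P(no change) is the sum over k = 0 to 3 of P(k, 2k).

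- p = 0.25, ρ = 0.6 (α = 0.167, β = 0.5): 0.529 + 0.024 + 0.019 + 0.081 = 0.654 (unrounded sum 0.6535).
- p = 0.50, ρ = 0.6 (α = β = 0.333): 0.243 + 0.029 + 0.029 + 0.243 = 0.545 (unrounded sum 0.5445).

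| ρ | Detection | Decreased | No change | Increased | Changed | Of 51 |
|---|---|---|---|---|---|---|
| 0.6 | 25% | 16.7% | 65.4% | 18.0% | 35% | 17.7 |
| 0.6 | 50% | 22.8% | 54.5% | 22.8% | 46% | 23.2 |
| 0.8 | 25% | 8.8% | 82.1% | 9.1% | 18% | 9.1 |
| 0.8 | 50% | 11.9% | 76.2% | 11.9% | 24% | 12.1 |

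The sums for ρ = 0.6 show that most unchanged labels come from children who are negative throughout (k = 0) or positive throughout (k = 3).

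**3. Concentration label with no true change.** If non-detects are coded to one value, a tie needs nine non-detects. At ρ = 0.6 that probability is 0.529 (25% detection) or 0.243 (50%). The share labelled changed is 1 − 0.529 = 47% or 1 − 0.243 = 76%.

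**4. The lean.** On frequency at ρ = 0.6 it is 18.0 − 16.7 = 1.3 points at 25% detection and nil at 50%. At ρ = 0.8 it is 9.1 − 8.8 = 0.3 points at 25%. On concentration, simulation at ρ = 0.6 with lognormal positives (sigma 1, an assumption) gives 27.2% increased v 20.0% decreased at 25% detection, and 42.8% v 32.8% at 50%. That is 7 to 10 points. It arises because the mean of six skewed values is more likely to include a high value than the mean of three.

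**5. Effect of a margin.** At ρ = 0.6, allowing a difference of up to 1/6 as no change cuts the false frequency labels to 17% (25% detection) or 23% (50%). Allowing up to 1/3 cuts them to 6% or 8%. With either margin the frequency lean at 25% detection is no longer towards increased.

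**6. What adjustment gains.** In units of the single-sample variance at ρ = 0.6, the run-in mean has variance 0.6 + 0.4/3 = 0.733, the later mean has 0.6 + 0.4/6 = 0.667, and their covariance is 0.6. The raw change has variance 0.733 + 0.667 − 1.2 = 0.200. Adjusting the later mean for the run-in mean leaves 0.667 − 0.36/0.733 = 0.176, which is 12% less.

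**The case against.** The strongest reply is that the Protocol states no zero margin. It names three categories, and a cut-off for a derived category commonly sits in a statistical analysis plan, which is not at hand. This stands: every percentage for the labels depends on the assumed margin, and a margin of 1/3 removes most of the problem on frequency.

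Second, the numerical change is retained, and its mean is zero when nothing has changed, at any detection rate or correlation. This also stands. The labels are an addition, and a reader who inferred that they replace the continuous analysis would be wrong.

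Third, both arms have the same sample counts, so with equal underlying rates noise and lean are the same in each. A reader might infer that the labels bias the randomized comparison. With no true change they do not, and the blinded arm shows the background level.

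Fourth, a reader might infer a marked lean towards increased at low detection. On frequency that needs a child's samples to be near independent: with one common rate of 10% the split is 34.5% v 24.3%. The Protocol plans on neither that rate nor that correlation.

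What survives is narrower. The three labels are planned output with no margin in the text, and the outcome's per-individual wording invites within-arm readings that chance could largely produce.

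**Conclusion.** The point holds in limited form. With a zero margin and complete samples, chance alone labels 35% to 46% of unchanged children as changed on frequency at the plan's ICC of 0.6, and 18% to 24% at 0.8. On concentration it is 47% to 76% at 0.6 if non-detects share one value. The lean to increased is negligible on frequency at the plan's correlations. On concentration it is about 7 to 10 points, but only under the assumed lognormal spread. The primary outcome is untouched, and so is the continuous form of this secondary outcome. The damage is confined to within-arm statements and to any comparison based on the labels. Severity is minor to moderate.

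**What to change.** In section H (Secondary outcomes), remove the three-way categorization, or keep it as description only with a prespecified margin for no change on each scale. Make the secondary analysis the between-arm difference in the post-randomization proportion of positive urines, and likewise in mean concentration, adjusted for the child's own run-in value and reported with a 95% confidence interval. Show individual change as a plot by arm.

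This needs a paragraph of wording and no new data, since the run-in urines are already collected. The cost is the loss of a simple three-row table. If the labels stay with a margin, some small true changes will be counted as no change.

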During week 8, participants will bring samples collected at home and completed questionnaires to the second study visit along with an additional stool sample taken at the week 8 time point. At this time, there will be a blood draw and participants will be randomized to continue with double-blinded test results or an open results arm. Randomization will be stratified based upon the results of GIP testing in stool collected at week 8 to ensure that participants with documented gluten exposure are distributed equally between the blinded and open results arms. Participants in the open results arm will receive instruction in using home test kits for detection of GIPs and supplied with test kits to be used at home during the remainder of the study period. Participants will be given a parking voucher and receive a \$30 ClinCard as a token of appreciation. All participants will also have a diet assessment by a Registered Dietitian either in person or remotely by telephone or video link in conjunction with the week 8 study visit.

During weeks 8 through 30, participants will keep a diary of any suspected gluten exposures. Participants will be contacted by the study co-ordinator at random intervals (approximately every three to four weeks) and instructed to collect their next urine and complete the symptom questionnaire. Participants in the open results arm will also perform home testing and send a photo of the test results to the study co-ordinator to document results and confirm test completion. Used test kits may be disposed in household trash. Participants will also test up to 4 stool samples during this time that will be collected and tested at the discretion of the participant. Participants will report date of use, results,

and reason for use after each home stool test. Participants will return all other study materials and containers at the final study visit.

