## **H. Data Analysis Plan**

For all outcomes, descriptive data analysis will be used to assess variables' distributions and to detect outliers and influential observations. We will estimate means (and standard deviations) and medians (and interquartile ranges) of continuous variables, and proportions of categorical variables. In addition, we will examine the data using plots, such as boxplots, histograms and smoothed-scatterplots. When necessary, variables will be transformed to meet assumptions for statistical tests. All statistical tests will be two-sided and will use a Type I error of 5%. For confidence intervals, we will use two-sided 95% coverage probabilities.

As a general approach, all proportions will be reported as mean with the associated 95% confidence interval for the estimate. This will provide more meaningful information about the precision of each estimate as well as the possible clinical significance of any observed differences in the mean value. As such, p values for comparisons of means will not be determined with the implicit assumption that values for which the 95% confidence intervals overlap do not differ significantly. Relationships between continuous measures will be analyzed using Pearson's correlation coefficient. Where appropriate,

continuous measures will also be converted to categorical variables (e.g., serum antibody negative/positive vs. GIP negative/positive).

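### A paired t-test is assigned to blinded-versus-open comparisons of symptom and quality-of-life scores, although the two arms are independent groups of children (secondary outcomes only)

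*Protocol*

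**What the plan says.** Section H, under secondary outcomes, names one test for these scores: "Symptom and quality of life scores are also continuous variables and group comparisons will be assessed using a paired t-test". No other test is named for them.

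Section D(4) lists the outcomes it would serve:

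- Symptoms after randomization: "Symptom score (average for weeks 8 through 30 and at week 30) with blinded vs. open results of biomarker detection".
- Symptoms against the run-in: "Symptom score (average during run-in compared to week 30) with blinded vs. open results of biomarker detection".
- Disease-specific quality of life (CDDUX): change "between weeks 1 and 30 in blinded vs. open results groups".
- Generic quality of life: "Change in health related quality of life between weeks 8 and 30 as measured by PedsQL core 4.0", also blinded against open.

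On allocation, Section D(5) says: "Randomization will be stratified based upon the results of GIP testing in stool collected at week 8". Each child goes to one of two parallel arms.

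The opening of Section H sets two general rules. All tests are two-sided at 5%. It also says that "p values for comparisons of means will not be determined", and that overlapping 95% intervals will be taken to mean no significant difference.

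**The concern.** A paired t-test needs each observation in one set to have a natural partner in the other. Children in the blinded arm have no partners in the open arm. Stratifying on the stool result balances the arms but creates no pairs.

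The natural way to run a paired test here is before against after, within each arm. That answers a different question. Aims 2(c) and 2(d) in Section A ask whether knowing the biomarker results affects symptoms and quality of life, and only a contrast between arms addresses that. Change in both arms without any effect of disclosure is plausible. Section D(5) explains the run-in as time for behavior to shift after the clinician visit and under monitoring, and every child has a dietitian assessment at week 8. The risk is greatest for the two outcomes whose starting point lies before week 8 (CDDUX from week 1, and symptoms from the run-in). It is smaller for PedsQL, which starts at week 8, so that mainly the dietitian assessment remains as a common influence.

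At stake is a possible report that disclosure works because the open arm changed significantly and the blinded arm did not, with no test of the difference itself.

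**Working it through.** **The plan's own figure.** The protocol gives no power or sample size for symptoms or quality of life. Its nearest figure is for the primary outcome (Section I: 51 per arm, 50% against 25%, six samples per child).

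- ICC 0.6: design effect 1 + 5 × 0.6 = 4.0; effective n per arm 51 × 6 / 4.0 = 76.5; power 89.9% (stated 90%).
- ICC 0.8: design effect 5.0; effective n 61.2; power 82.3% (stated 82%).

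Both reproduce, and neither depends on the paired t-test.

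**Does the test fit each outcome?**

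| Outcome (Section D(4)) | Pair within a child? | Does a paired test compare arms? |
|---|---|---|
| Symptom average weeks 8–30, and week-30 score | No baseline in the definition | No |
| Symptoms, run-in against week 30 | Yes | No, only change within an arm |
| CDDUX, weeks 1 to 30 | Yes | No, only change within an arm |
| PedsQL, weeks 8 to 30 | Yes | No, only change within an arm |

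**Size of the risk if within-arm verdicts are compared.** Suppose both arms truly change by the same amount, and each within-arm test has power p. The arms are independent, so P(open significant, blinded not) = p(1 − p).

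- p = 0.5: 0.5 × 0.5 = 25%, the maximum of this expression.
- p = 0.8: 0.8 × 0.2 = 16%.

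**Simulation as a check.** Two independent arms of 51, no arm effect, 20,000 runs per scenario. The pre-post correlation (0.3 to 0.7) and the common shift (0 to 0.5 SD) are assumptions, since the protocol gives neither. The last column is half of the second, by symmetry.

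| Common shift | Exactly one arm significant | Open arm alone |
|---|---|---|
| 0 | 9.5% to 9.8% | about 5% |
| 0.3 SD | 36% to 49% | 18% to 25% |
| 0.5 SD | 1% to 27% | 0.5% to 13% |

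The risk falls at the largest shift because both arms are then usually significant. A two-sample t-test on change scores kept its type I error at 4.9% to 5.3% throughout.

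**Does the interval-overlap rule supply the missing test?** With equal standard errors SE, two 95% intervals fail to overlap only when the difference exceeds 2 × 1.96 × SE. The difference has standard error √2 × SE, so this requires z = 3.92 / 1.414 = 2.77, a two-sided p of about 0.006. The rule is far stricter than the 5% level declared in the same section.

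**Precision of the proposed analysis.** Per unit of outcome variance, with pre-post correlation r, ANCOVA leaves 1 − r² and a change score leaves 2(1 − r). The ratio is (1 + r)/2, so the variance reduction is (1 − r)/2: 35% at r = 0.3, 25% at r = 0.5, 15% at r = 0.7 (r assumed). The finding does not rest on this.

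**The case against.** The benign reading is that the word paired refers to before and after in the same child. Three of the four listed outcomes do have that element. But the sentence assigns the test to group comparisons, each outcome is set against the other arm, and the post-randomization symptom endpoint has no before.

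A reader might infer that these aims are left with no between-arm comparison at all. The protocol does not support that: the interval-overlap rule in Section H is a between-arm comparison of a kind. It is crude and conservative, and its statement that p values for means will not be determined contradicts naming any t-test. It therefore adds a conflict and does not cure the error.

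A reader might also infer that the investigators intend to compare within-arm verdicts. The protocol nowhere says so; that is an inference from the test named. Nor should discordance in either direction (50% at p = 0.5, 32% at p = 0.8) be quoted as the chance of a false claim for disclosure. Only half of it favors the open arm.

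A paired test could also be run by pairing children across arms arbitrarily. In the simulation this kept type I error near 5%. It has no basis in the design, needs equal arm sizes, and cuts the degrees of freedom from 100 to 50, but it would not generate false positives.

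Finally, a separate statistical analysis plan may exist. That would excuse silence in the protocol, but not a wrong test named in it.

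**Conclusion.** The paired t-test is the wrong test for these comparisons as the protocol defines them. This follows from setting Sections D(4), D(5) and H side by side and needs no assumption. It affects the symptom and quality-of-life outcomes only; the primary outcome, its power, the randomization and the data collection stand. It should be fixed, but reading it as a threat to the trial's main conclusion would go beyond the document.

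The size of the harm is conditional. If within-arm verdicts were compared and both arms changed equally, a false appearance of benefit in the open arm alone would arise in 25% of trials at 50% within-arm power and in 16% at 80%. It could be much lower if the common change is very small or large. With no SD, shift or correlation in the protocol, these figures are illustrative.

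**What to change.** In Section H, replace the paired t-test with an independent-groups comparison. The preferred form is ANCOVA of the week-30 score on arm (for the post-randomization symptom outcome, also the mean over weeks 8 to 30), adjusted for the week-8 stool GIP stratum and for the baseline that Section D(4) sets for each endpoint:

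- CDDUX: week 1.
- PedsQL: week 8.
- Symptoms: run-in average. For the post-randomization symptom outcome, which has no baseline in its definition, this enters only as a covariate.

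A two-sample t-test would also cure the defect; ANCOVA is preferred for precision. Report the between-arm difference with its 95% CI and p value, and keep within-arm changes descriptive.

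In the same edit, amend the general rule in Section H so that it no longer rules out p values for comparisons of means or uses interval overlap as the criterion.

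The cost is a few sentences of text. The questionnaires at each study visit and during the run-in, and the week-8 stool result, are already scheduled. The sample size does not change.
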